## **6.10 Concomitant Medication Assessments**

The Investigator or designee will record any concomitant therapies given during the course of the study on the concomitant medication page of the subject's source documentation and eCRF. Any changes in concomitant therapy during the study will also be documented, including cessation of therapy, initiation of therapy, and dose changes.

Concomitant therapies are defined as prescribed medications and over the counter (OTC) preparations, including herbal preparations and vitamins, other than study medication and supplementary medication that the subject receives within 28 days of screening and for the during the course of the study. Any medication taken by the subject is to be reported by the subject and noted on the subject's source document and concomitant medication page. Any changes in concomitant therapy during the study will be documented, including cessation of therapy, initiation of therapy, and dose changes.

Subjects who are medically prescribed benzodiazepines will be evaluated on a case-by-case basis for inclusion in the INDV-6000-301 study. The Investigator will discuss these subjects with the Medical Monitor before enrolling into the INDV-6000-301 study.

The Investigator or designee will also record any medications given for the treatment of AEs on the concomitant medication page.

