9.3 PRIOR AND CONCOMITANT MEDICATIONS

Prior and concomitant medications will be categorized by preferred name and drug category class (CMCLAS, ATC level 4 class per World Health Organization Drug Dictionary [WHODRUG]); and will be summarized for the Safety Analysis Set. The number and percentage of subjects using each medication will be displayed together with the number and percentage of subjects using at least one medication.

Prior medications rolling over from prior studies will be considered for both prior and concomitant medications in this study.

Prior Medications

For a subject in the Safety Analysis Set, prior medications will include any medication taken within 28 days prior to subject's first dose of RBP-6000 in the INDV-6000-301 study.

Concomitant Medications

Concomitant medications are defined as prescribed medications and Over The Counter (OTC) preparations, including herbal preparations and vitamins, other than RBP-6000.

All prior medications will be presented in separate listing for the Safety Analysis Set.

A summary of all concomitant medications taken from Day 1 to last dose + 28 days will be presented as during RBP-6000 dosing for the Safety Analysis Set.

A summary of all concomitant medications taken from the last dose + 29 days to the last recorded assessment will be presented as post RBP-6000 dosing for the Safety Analysis Set.

A listing of all subject's concomitant medications during RBP-6000 dosing and post RBP-6000 dosing will be listed separately.

After imputing the incomplete start/end date of non-study medications (as described in Section 20.8), the determination of concomitant medication during vs. post RBP-6000 dosing follows the rules in the [Table 1](#) below.

Table 1: Determination of Concomitant Medication during vs. Post RBP-6000 dosing

		Start date of Non-Study Medication			
		missing	Prior to day 1	from Day 1 to last dose +28 days (inclusive)	Post last dose+28 days
End date of non-study medication	missing	During ¹ , Post ²	During, Post	During, Post	Post
	from Day 1 to last dose +28 days (inclusive)	During	During	During	Data error
	Post last dose+28 days	During, post	During, post	During, post	post

¹ during RBP-6000 dosing. ² post RBP-6000 dosing

CNS Depressants

If a subject satisfies any of the three criteria below, then the subject is classified as taking a CNS Depressant

Criterion 1:

[INDV-6000-301] SAP Version 1.0

October 6, 2017

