Subject with concomitant medication and its class (CMCLAS) in ('BENZODIAZEPINE RELATED DRUGS' 'BENZODIAZEPINE DERIVATIVES' 'DIAZEPINES, OXAZEPINES, THIAZEPINES AND OXEPINES' 'OTHER HYPNOTICS AND SEDATIVES' 'PHENOBARBITAL'). Defined in the later section (CNS Depressant Medication Categories)

Criterion 2:

Subject with substances 'Barbiturates' or 'Benzodiazepine' detected positive in Urine Drug Screen during the Treatment Period.

CNS Depressant Medication Categories

Benzodiazepine-related drugs

If the Concomitant medication class is "BENZODIAZEPINE RELATED DRUGS" or detection of substances "Benzodiazepine" positive in Urine Drug Screen positive during the Treatment Period, then it is derived as Benzodiazepine related drugs.

Benzodiazepine derivatives

If the Concomitant medication class contains ("BENZODIAZEPINE DERIVATIVES", "DIAZEPINES, OXAZEPINES, THIAZEPINES AND OXEPINES") during the Treatment Period then it is derived as Benzodiazepine Derivatives.

Other Hypnotics and Sedatives

If the Concomitant medication class is ("OTHER HYPNOTICS AND SEDATIVES") during the Treatment Period, then it is derived as Other Hypnotics and Sedatives.

Phenobarbital and Derivatives

If the Concomitant medication class is "PHENOBARBITAL" during RBP-600 dosing or detection of substances Barbiturates positive in Urine Drug Screen during the Treatment Period, then it is derived as Phenobarbital and Derivatives.

Summary of subjects who have taken CNS depressant medications during RBP-6000 dosing (from Day 1 to last dose + 28 days) be provided. CNS depressant medications can be indemnified from two sources in this study: Concomitant medications or Urine Drug Screen as in the table below ([Table 2](#)).

Table 2: Summary of Subjects Who Have Taken CNS Depressant Medications During RBP-6000 Dosing

Any CNS depressant (from Concomitant medications) taken with a start date after Day 1 to last dose + 28 days
Benzodiazepine-related Drugs Benzodiazepines Derivatives Other Hypnotics and Sedatives Phenobarbital and Derivatives
Any positive CNS depressant (from UDS) during the treatment period
Barbiturate Positive Benzodiazepines Positive

Preferred terms at drug class ATC level 3 of drug categories Benzodiazepine-related Drugs, Benzodiazepines Derivatives, Other Hypnotics and Sedatives and Phenobarbital and Derivatives will be summarized in the safety analysis set (see Appendix 1 for the list of CNS depressant medications).

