11.0 EXPLORATORY EFFICACY ANALYSES

11.1 URINE DRUG SCREEN (UDS)

The urine sample collected at Screening visit will be tested for drugs listed in the [Table 3](#). The drugs classified as opioids are identified in the same table.

Table 3: Opioid Drug Classification in Urine Drug Screen at Screening Visit.

Drug	Opioid?
Amphetamine	No
Barbiturates	No
Benzodiazepine	No
Benzoylecggonine (Cocaine metabolite)	No
Cannabinoids	No
Opiates	Yes
Codeine	Yes
Hydrocodone	Yes
Hydromorphone	Yes
Methadone	Yes
Morphine	Yes
Oxycodone	Yes
Oxymorphone	Yes
Methamphetamine	No
Phencyclidine	No

At Screening, specific substances were confirmed once the test for Opiates was positive. The UDS for Opioids at Screening will be defined as follows:

The UDS for Opioids is Non-negative at Screening if at least one UDS result (listed in Table) is positive;

The UDS for Opioids is Negative at Screening, if all non-missing UDS results for opioids are negative.

If all UDS measurements for opioids are missing at Screening, the UDS for Opioids will be classified as missing; then be imputed as Non-negative; and be flagged as “Non-Responder Imputation”.

The urine sample collected at visits in the Treatment Period will be tested for drugs listed in the [Table 4](#). The drugs classified as opioids are identified in the same table.

Table 4: Opioid Drug Classification in Urine Drug Screen at visits in the Treatment Period

Drug	Opioid?
Amphetamine	No
Barbiturates	No
Benzodiazepine	No
Benzoylecgone (Cocaine metabolite)	No
Cannabinoids	No
Opiates	Yes
Methadone	Yes
Oxycodone	Yes
Methamphetamine	No
Phencyclidine	No

Different from Screening Visit, specific opiate substances were not confirmed when the Opiates test was positive. Samples were tested for Oxycodone and Methadone separately from the Opiates test.

The UDS for Opioids at visits in the Treatment Period will be defined as follows:

The UDS for Opioids is Non-negative at visits in the Treatment Period if at least one UDS result (listed in Table 4; either the Opiates test, or individual test for Methadone or individual test for Oxycodone) is positive;

The UDS for Opioids is Negative at visits in the Treatment Period, if all non-missing UDS results for opioids are negative.

If all UDS measurements for opioids are missing at visits in the Treatment Period, the UDS for Opioids will be classified as missing; and then be imputed as Non-negative; and be flagged as “Non-Responder Imputation”.

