20.8 MISSING DATE INFORMATION FOR CONCOMITANT MEDICATIONS

For concomitant medications, incomplete (i.e., partial missing) start date and/or stop date will be imputed. When the start date and the stop date are both incomplete for a subject, consider to impute the start date first.

Missing day and month

- If the year of the incomplete start date is the same as the year of the date of the first dose of investigational product, then the day and month of the date of the first dose will be assigned to the missing fields.
- If the year of the incomplete start date is before the year of the date of the first dose of investigational product, then December 31 will be assigned to the missing fields.
- If the year of the incomplete start date is after the year of the date of the first dose of investigational product, then January 1 will be assigned to the missing fields.

Missing month only

- The day will be treated as missing and both month and day will be replaced according to the above procedure.

Missing day only

- If the month and year of the incomplete start date are the same as the month and year of the date of the first dose of investigational product, then the day of the first dose will be assigned to the missing day.
- If either the year is before the year of the date of the first dose of investigational product or if both years are the same but the month is before the month of the date of the first dose of investigational product, then the last day of the month will be assigned to the missing day.
- If either the year is after the year of the date of the first dose of investigational product or if both years are the same but the month is after the month of the date of the first dose of investigational product, then the first day of the month will be assigned to the missing day.

Incomplete Stop Date

Missing day and month

- If the year of the incomplete stop date is the same as the year of the date of the last dose of investigational product, then the day and month of the date of the last dose will be assigned to the missing fields.
- If the year of the incomplete stop date is before the year of the date of the last dose of investigational product, then December 31 will be assigned to the missing fields.
- If the year of the incomplete stop date is after the year of the date of the last dose of investigational product, then January 1 will be assigned to the missing fields.

Missing month only

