14.1 Demographic Data Tables & Figures

Table 14.1.1.1 Subject Disposition – All Screened Subjects
Table 14.1.1.2 Enrollment by Site – All Screened Subjects
Table 14.1.1.3 Enrollment by Site - Safety Analysis Set
Table 14.1.1.4 Subject Analysis Sets - All Screened Subjects
Table 14.1.2.1 Demographic and Baseline Characteristics – Safety Analysis Set
Table 14.1.3.1 Medical History - Safety Analysis Set
Table 14.1.4.1 Substance Use – Safety Analysis Set
Table 14.1.5.1 Summary of Prior Medications – Safety Analysis Set
Table 14.1.5.2 Summary of Concomitant Medications during RBP-6000 Dosing – Safety Analysis Set
Table 14.1.5.3 Summary of Concomitant Medications post RBP-6000 Dosing– Safety Analysis Set
Table 14.1.5.4 Summary of Subjects Who have taken CNS Depressant Medications during RBP-6000 Dosing (using Concomitant medication data and Urine Drug Screening)– Safety Analysis Set
Table 14.1.5.5 Summary of CNS Depressant Medications Taken during RBP-6000 dosing – Safety Analysis Set
Table 14.1.5.6 Summary of CYP3A4 Inhibitor Medications by Category (Unclassified, Weak, Moderate or Strong inhibitors) during RBP-6000 dosing – Safety Analysis Set
Table 14.1.5.7 Summary of CYP3A4 Inhibitor Medications by Category (Unclassified, Weak, Moderate or Strong inhibitors) post RBP-6000 dosing – Safety Analysis Set
Table 14.1.6.1 Summary of RBP-6000 Exposure – Safety Analysis Set
Table 14.1.6.2 Cumulative Frequency Distribution of RBP-6000 Exposure – Safety Analysis Set
Table 14.1.6.3 Summary of RBP-6000 Injections – Safety Analysis Set
Table 14.1.6.4 Cumulative Frequency Distribution of RBP-6000 Injections – Safety Analysis Set
Table 14.1.6.5 Dose Level Over Time During the Treatment Period – Safety Analysis Set
Table 14.1.6.6 Dose Level Over Time During the Treatment Period for Subjects Who Received 100 mg at the First Injection – Safety Analysis Set
Table 14.1.6.7 Dose Level Over Time During the Treatment Period for Subjects Who Received 300 mg at the First Injection – Safety Analysis Set
Table 14.1.6.8 Dose Modification and its Reason Over Time During the Treatment Period – Safety Analysis Set
Figure 14.1.6.8 Stacked Bar Chart of Dose Modification Over Time During the Treatment Period – Safety Analysis Set
Table 14.1.6.9 Frequency Distribution of Total Number of Injections in the Treatment Period by Dose Level – Safety Analysis Set
Table 14.1.6.10 Frequency Distribution of Days Since Last Injection During the Treatment Period – Safety Analysis Set

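### SAP Table 2 counts a CNS depressant from medication records only if it was started after Day 1, so continuing users are left out of a table meant to count use during dosing

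*SAP*

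**What the plan says.** SAP Section 9.3 defines the dosing period for concomitant medications by use: anything taken between Day 1 and 28 days after the last dose is reported as during dosing. Table 1 of the SAP then decides between during and post from the start and end dates. A start before Day 1 gives During whether the end date is missing, inside the window or after it. A missing start date gives the same result in all three rows, and the start-date window includes Day 1. On medications carried over from the parent studies, the section says: "Prior medications rolling over from prior studies will be considered for both prior and concomitant medications in this study".

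For CNS depressants, the sentence introducing Table 2 keeps to use: "Summary of subjects who have taken CNS depressant medications during RBP-6000 dosing (from Day 1 to last dose + 28 days) be provided". The titles of Table 2 and of output Table 14.1.5.4 carry no start-date limit, and neither does Criterion 1, which classifies by medication class. Only the concomitant-medication row of Table 2 differs: "Any CNS depressant (from Concomitant medications) taken with a start date after Day 1 to last dose + 28 days".

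Protocol Section 6.10 makes continuing use foreseeable: "Subjects who are medically prescribed benzodiazepines will be evaluated on a case-by-case basis for inclusion in the INDV-6000-301 study".

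**The concern.** A programmer who follows the row label will filter on the start date. One who follows Table 1 will not. Both could defend their program from the SAP, and the two would report different numbers of users.

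The subjects lost under the row label are those one would expect in an extension study. Every subject enters on the day of the RB-US-13-0003 end-of-study visit, so a medication in use at that point normally has a start date before Day 1. Protocol Section 6.10.1 asks for careful monitoring when benzodiazepines or sedative/hypnotics are used, and the SAP summarises CNS depression and respiratory depression events separately. Table 14.1.5.4 is the planned subject-level count of CNS-depressant co-use that draws on both medication records and urine screening. An undercount there would give a reader too low a figure for co-use, and the table could disagree with Table 14.1.5.2 for the same subjects.

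**Working it through.** No sample-size, power or error-rate figure is involved, and the plan gives no figure of its own to reproduce. The check compares the Table 2 row with Table 1.

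**Inputs.** SAP Section 9.3, Tables 1 and 2; SAP Section 20.8 for partial dates; SAP Section 11.1, Table 4, for the urine panel; the Protocol Schedule of Events for the day of the sixth injection (Day 141).

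**Step 1: cells of Table 1.** There are 4 start-date columns and 3 end-date rows, so 4 × 3 = 12 cells.

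| Start date | Cells classed During (of 3) | Reached by the Table 2 row |
|---|---|---|
| Missing | 3 | 0 |
| Before Day 1 | 3 | 0 |
| Day 1 to last dose + 28 | 3 | 3 (except Day 1 itself) |
| After last dose + 28 | 0 | 0 |

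During cells: 3 + 3 + 3 = 9. Reached by the row: 3. Dropped: 9 − 3 = 6.

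**Step 2: day-level check.** Take the last dose on Day 141, so the window ends on Day 141 + 28 = Day 169. Table 1 counts a medication if it starts by Day 169 (or the start is missing) and ends on or after Day 1 (or the end is missing). The Table 2 row counts it if Day 1 < start ≤ Day 169.

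| Start | End | During by Table 1 | Counted by Table 2 row |
|---|---|---|---|
| Day −200 | missing, Day 60 or Day 190 | Yes | No |
| Missing | missing or Day 60 | Yes | No |
| Day 1 | missing or Day 30 | Yes | No |
| Day 2 | Day 30 | Yes | Yes |
| Day 100 or Day 169 | missing | Yes | Yes |
| Day 170 | missing | No | No |

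**Step 3: partial start dates.** When only the year is known and it is the year of first dose, Section 20.8 says "then the day and month of the date of the first dose will be assigned to the missing fields"; a start date lacking only the day, in the month of first dose, is handled the same way. With an assumed first dose on 15 March 2017, a start recorded as 2017 becomes 15 March 2017, which is Day 1. Table 1 includes that date; a strict reading of the Table 2 row excludes it.

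**Step 4: what urine screening recovers.** Table 4 of Section 11.1 lists 10 tests in the Treatment Period. Two, barbiturates and benzodiazepine, are CNS-depressant classes. A continuing user of either who tests positive appears in the urine rows and meets Criterion 2. No test covers other hypnotics and sedatives.

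**Step 5: illustration only.** The documents give no rates. Assume 300 subjects, a share p of continuing users from 2% to 10%, and a separate share q of subjects starting after Day 1 from 1% to 5%. Table 1 counts 300 × (p + q), which runs from 9 to 45. The Table 2 row counts 300 × q, from 3 to 15. The share missed is p / (p + q): lowest at 2 / 7 ≈ 29% and highest at 10 / 11 ≈ 91%, before any recovery through urine screening.

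**The case against.** The strongest reply is that the phrase is a loose row label. It occurs once, the correct rule is stated elsewhere in the same section, and a careful programmer would apply Table 1. That may be what happens, but nothing in the SAP says the label is informal, and it names the variable to filter on.

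Second, the information is not lost. Continuing users remain in Table 14.1.5.2 and Listing 16.2.11.1, and the title of Table 14.1.5.5, which summarises CNS-depressant medications during dosing, has no start-date limit either. This stands and limits the consequence. It also means that the tables could visibly disagree.

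Third, 6 of 9 cells is not a measure of subjects. The cells are not equally populated, and the missing-start column holds only dates still missing after the Section 20.8 imputation. This stands too: the cell count shows how far the rule departs from Table 1, and the percentages in the illustration rest wholly on assumed rates.

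Fourth, the category definitions in Section 9.3 place a positive benzodiazepine screen under benzodiazepine-related drugs and a positive barbiturate screen under phenobarbital and derivatives, so two of the four sub-rows may pick up screen-positive subjects whatever their start date. That is correct, but it does nothing for users who test negative or for other hypnotics and sedatives.

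Finally, the sponsor may have wanted new starts only. The table title would then be wrong and continuing users would need their own row, so the text needs correcting on either reading.

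**Conclusion.** The concern holds. The Table 2 row contradicts Table 1, the roll-over rule, its own introductory sentence and the table title. Followed as written, it omits continuing users, missing start dates and Day 1 starts, which is 6 of the 9 During cells and part of the other 3. The direction is downward; the number of subjects cannot be derived from the documents. The conclusion assumes that the row is programmed literally and that at least some subjects were taking a CNS depressant on entry.

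The consequence is confined to one descriptive table: no hypothesis test or denominator depends on it, and the underlying records are reported elsewhere. It should be corrected because it is a stated rule that gives the wrong count, not merely an absence of detail.

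**What to change.** Reword the Table 2 row to: CNS depressant (from concomitant medications) taken at any time from Day 1 to last dose + 28 days, classified as During by Table 1, whatever the start date. Confirm that Table 14.1.5.5 uses the same rule. If new starts are of separate interest, show them as an additional labelled row beside continuing users.

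In the same edit, settle these points in Section 9.3:

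- The text announces three criteria ("If a subject satisfies any of the three criteria below, then the subject is classified as taking a CNS Depressant") but lists two. State the third or correct the number.
- It refers to Appendix 1 for a list of CNS-depressant medications, but that appendix holds adverse-event preferred terms. Supply the list or point to the drug classes in Criterion 1.
- Say whether positive urine screens feed the medication sub-rows or only the urine rows, and which window applies. Section 20.1 ends the Treatment Period at the later of the EOS/ET visit and last injection + 28 days, so it can run beyond the dosing window.

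The main correction costs one line of SAP text and one filter change, with no new data. The reported number of users may rise.

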10.0 EXTENT OF EXPOSURE AND TREATMENT COMPLIANCE

10.1 EXTENT OF EXPOSURE

Exposure duration is defined as the date of last injection + 28 days - the date of first injection +1.

A summary of the exposure to RBP-6000 during the treatment period will be summarized by visit and dosage for the Safety Analysis Set. A listing of RBP-6000 exposure (administration/dispensation) will be provided.

The duration of exposure in 4 week intervals (i.e., 0 - <4 weeks, 4 - <8 weeks through 20 - <24 weeks and >= 24 weeks), total number of RBP-6000 doses received, the total number of actual doses as a continuous summary, and the total number of actual doses as a categorical summary will be presented by dose received in the Safety Analysis Set. RBP-6000 exposure data will also be listed detailing the dose of RBP-6000 received at each injection and days since last injection. Besides, the cumulative frequency distribution will be tabulated by categories of >0 weeks, >=4 weeks through >=24 weeks.

The number of subjects who had an early surgical removal of the RBP-6000 depot will be presented for the Safety Analysis Set and by dose level (i.e., either 100 mg or 300 mg). Early surgical removal of the study drug depot data including the reason and surgical removal date and time will be listed, if surgical removal of the RBP-6000 depot occurs within the study.

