## 1.2 Rationale for Dose Selection

The doses proposed in this study are 100 mg RBP-6000 and 300 mg RBP-6000, which are the doses subjects are currently receiving in the RB-US-13-0003 study. These doses were chosen in the RB-US-13-0001 and RB-US-13-0003 studies as modeling and simulation ([Nasser 2014](#)) demonstrated that the 300 mg SC dose is an appropriate dose to assess for efficacy. The 100 mg RBP-6000 dose is provided because it is recognized that some individuals may need or desire lower dosages.

Doses of RBP-6000 may be adjusted up or down (to either 100 mg or 300 mg) throughout the course of the study based on the medical judgment of the Investigator.

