### **6.12.1 Early Removal of RBP-6000**

In the event of an emergency, toxicity is suspected, or if a subject withdraws or is withdrawn within the first 14 days of receiving an injection of RBP-6000, subjects may have the option to have the depot surgically removed by a physician delegated to perform surgery. The medically responsible physician should carefully discuss this option with subjects and the feasibility of

extracting the depot. The surgical procedure requires a small incision in the abdomen where the depot was placed, removal of the depot with forceps, and suturing to close the incision. The subject should have the ET assessments performed at the time of early removal of RBP-6000 and a safety follow up call 28 days later, as per the SOE ([Appendix 1](#)).

The extracted RBP-6000 depot will be disposed as per the SOPs at the clinical site.

Detailed RBP-6000 depot removal instructions are in [Appendix 2](#).

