6.2 SAFETY ANALYSIS SET

The Safety Analysis Set consists of all subjects who received at least one dose of RBP-6000.

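### SAP 10.1 defines exposure duration with no term for depot removal or dose, so removed depots are over-credited, the lowest category is always empty, and duration by dose is undefined for subjects who switch

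*SAP*

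**What the plan says.** SAP 10.1 sets a single subject-level rule: "Exposure duration is defined as the date of last injection + 28 days - the date of first injection +1". It is applied in the Safety Analysis Set, defined in SAP 6.2: "The Safety Analysis Set consists of all subjects who received at least one dose of RBP-6000".

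The duration is to be tabulated in bands: "The duration of exposure in 4 week intervals (i.e., 0 - <4 weeks, 4 - <8 weeks" and so on, up to 24 weeks or more. The same sentence then lists the dose counts and closes with "the total number of actual doses as a categorical summary will be presented by dose received in the Safety Analysis Set". The paragraph before it also asks for an exposure summary by visit and dosage. For the cumulative table, "the cumulative frequency distribution will be tabulated by categories of >0 weeks, >=4 weeks through >=24 weeks".

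Two protocol features bear on this:

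- **Dose.** Section 1.2 says: "Doses of RBP-6000 may be adjusted up or down (to either 100 mg or 300 mg) throughout the course of the study". The choice is the Investigator's (section 5.4).
- **Depot removal.** Under section 6.12.1, in an emergency, on suspected toxicity, or on withdrawal within 14 days of an injection, "subjects may have the option to have the depot surgically removed by a physician delegated to perform surgery". Early-termination assessments are done at that time.

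SAP 10.1 counts subjects with a removal by dose level and lists the reason, date and time. It does not use the removal date in the duration. SAP 10.2 tabulates dose level by visit, dose over time by starting dose, and dose modifications, but no duration per dose.

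**The concern.** The protocol allows two events that change how long a subject is exposed, or to which dose: removal of the depot and a change of dose. The formula sees neither. It uses only the first and last injection dates and then adds a fixed tail.

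The study's sole objective is continued treatment with safety monitoring, so extent of exposure is one of its main descriptive outputs. Removal is tied to emergencies, suspected toxicity and early withdrawal, so the subjects whose exposure is overstated are ones a safety reader would look at. For duration by dose, the SAP asks for a display and gives no rule for it, so the programmer would have to invent one. Different inventions give very different figures for the same subject.

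**Working it through.** **Inputs.** The formula and bands are from SAP 10.1. The nominal injection days 1, 29, 57, 85, 113 and 141 are from Protocol Appendix 1. The spacing of 26 to 35 days is from Protocol 5.3. All day counts below are inclusive, as in the SAP.

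**Step 1. Check against the plan's own figure.** Six injections on schedule, no removal: 141 + 28 − 1 + 1 = 169 days (24.14 weeks). This matches the Day 169 end-of-study visit in Protocol 9.3. The formula is therefore right for a subject with an unremoved last depot, and right by dose if that subject stayed on one dose.

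**Step 2. Minimum value.** With one injection, last equals first: 0 + 28 + 1 = 29 days, and 29/7 = 4.14 weeks. Every subject in the Safety Analysis Set is therefore at or above 4 weeks. The 0 - <4 weeks row is zero by construction, and the >0 and >=4 weeks rows are both 100%. Dropping the +1 gives 28 days, exactly 4.00 weeks, so the row is still empty.

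**Step 3. Depot removal.** If the last depot is removed r days after injection, the formula overstates duration by 28 − r days.

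| Case | Reported | Days to removal | Overstated by |
|---|---|---|---|
| One injection, removed Day 3 | 29 | 3 | 26 |
| One injection, removed Day 8 | 29 | 8 | 21 |
| Six injections, removed Day 148 | 169 | 148 | 21 |

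The last case also changes band: 148/7 = 21.14 weeks, so the subject belongs in 20 - <24 weeks but is shown in >=24 weeks. These are calendar days to removal and make no claim about residual drug from earlier depots.

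**Step 4. Duration by dose.** The SAP states no rule. Two readings are compared on the nominal schedule:

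- *Within-dose:* apply the formula to the first and last injection at each dose.
- *Interval:* give each injection's days, up to the day before the next injection, to the dose injected. The last injection runs to +28 days.

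| Sequence (mg) | Within-dose 300 / 100 (sum) | Interval 300 / 100 (sum) |
|---|---|---|
| 300 ×6 | 169 / – (169) | 169 / – (169) |
| 300 ×3, 100 ×3 | 85 / 85 (170) | 84 / 85 (169) |
| 300, 100 ×4, 300 | 169 / 113 (282) | 57 / 112 (169) |
| 300, 100, 300, 100, 300, 100 | 141 / 141 (282) | 84 / 85 (169) |

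For the third row, within-dose 300 mg is 141 + 28 − 1 + 1 = 169 and 100 mg is 113 + 28 − 29 + 1 = 113. The interval figures are 28 + 29 = 57 and 4 × 28 = 112. The error on 300 mg is 169 − 57 = 112 days.

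For a single switch the error is 29 minus the spacing at the switch: +1 day at 28 days, +3 at 26 and −6 at 35.

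**The case against.** The strongest reply is that the split by dose may never have been meant for duration. The phrase ends a list whose last items are dose counts. SAP 6.3 defines one flexible-dose group. The titles of Tables 14.1.6.1 and 14.1.6.2 do not mention dose, whereas Table 14.1.6.9, on number of injections, does. On that reading there is no double counting. This reading is possible, but it is not the literal sentence, which opens with duration. The SAP should settle it.

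Time at each dose can also be approximated from what is planned: injections are 26 to 35 days apart, and SAP 10.2, Table 14.1.6.9 and the listings show dose by injection. That is true, and it limits the harm. It does not make a duration table correct.

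The 28-day tail is a consistent convention. It matches the release period in Protocol 5.2, the concomitant-medication window in SAP 9.3 and the Treatment End Date in SAP 20.1. Removals are disclosed. Shortening only the exposure variable would make it differ from the Treatment Period used for treatment-emergent events. This stands as a point the fix must address, but the convention assumes a depot still in place.

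Finally, an empty row shows a true zero and misleads no inference. That is fair, and on its own it would be minor.

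**Conclusion.** The definition needs amending. The empty lowest band is certain from the arithmetic. The over-credit is certain for any subject whose last depot is removed within 28 days of injection, and is at most 28 days per subject. The by-dose problem applies only if duration is shown by dose, and only to subjects who switch. Its size then depends on an unstated programming choice. Under the within-dose reading on the nominal schedule it runs from 1 day for a single switch to 112 days in the return-to-dose example.

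A reader might infer more than the documents support:

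- *That time on 100 mg and 300 mg will be misstated.* The SAP gives no per-dose rule, so the defect is that the split is undefined. The 282-day total assumes both the within-dose rule and a return to an earlier dose. Placing a subject's whole duration under each dose would give 2 × 169 = 338 days, but that is another unstated choice.
- *That safety results by dose rest on this duration.* They do not. Burning or stinging is a percentage of responses (SAP 12.4.4), attempted removal is a percentage of subjects by dose and visit (12.4.2), and surgical removal is a count of subjects (10.1). The adverse-event summaries in 12.1 count subjects, with no exposure-adjusted rate.

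The numbers of switchers and removals are not in the documents, so the effect on the tables as a whole cannot be sized. This is a defect in a descriptive exposure table, worth correcting because exposure is central to this study's purpose and the data needed are already planned for listing.

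**What to change.** Amend SAP 10.1 as follows:

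1. End overall exposure at the earlier of last injection + 28 days and the depot removal date. Otherwise keep the current first-to-last formula.
2. Decide whether duration is shown by dose. If so, give each injection's days (to the day before the next injection or, for the last injection, to the end date in item 1) to the dose injected, and sum within 100 mg and within 300 mg. If not, restrict the split by dose received to the dose counts.
3. Apply this in Tables 14.1.6.1 and 14.1.6.2. The 0 - <4 weeks row can then be populated by early removals. A footnote should say that a single injection without removal counts as 29 days.
4. State that exposure may now end before the Treatment Period used for treatment-emergent events, which is unchanged.

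The cost is SAP wording and one derived variable. Injection dates, doses and removal dates are already to be listed. Reported overall exposure falls slightly for subjects with a removal and does not change for anyone else. Nothing in the conduct of the study changes.
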